1. INTRODUCTION

1.1 Basic Information

Open angle glaucoma (OAG) is a chronic neurodegenerative disease characterized by the progressive loss of retinal ganglion cells and structural changes of the optic nerve head (1). It is the second leading cause of blindness in the world. The most common form, primary open-angle glaucoma, has as its main risk factor the increase in intraocular pressure for which the first therapeutic approach is represented by hypotonizing topical drugs. However, given that more than one third of patients under good blood pressure control delay, but do not stop the progression of visual impairment, other non-pressure dependent mechanisms are thought to be involved (2). In particular, following the primary insult, of a hyperbaric nature, apoptosis of the neuron is triggered, which interferes with the normal blood supply at the level of the capillary district of this structure, and the regular axonal transport is compromised, both antegrade and retrograde, of metabolites and neurotrophins essential for the survival of the ganglion cell (3). Then follows the secondary insult linked to the mechanisms of local excitation toxicity due to the hyperstimulation of NMDA receptors by the glutamate released by the cells in apoptosis (4). In fact, when present in excessive concentrations in the extracellular space, glutamate hyperstimulates the NMDA receptors on the surface of the surrounding neurons, which determine the opening of channels for Ca^{++} . The overflow of Ca^{++} ions into the cell represents the trigger of the biochemical cascade that will lead to apoptosis of the neuron itself, configuring a mechanism capable of self-feeding even in the absence of the primary insult (5). Another key step in the mechanism of cell damage during apoptosis is represented by the hyperactivation of phospholipase A2, an enzyme capable of destabilizing and disrupting the cell membrane through the catabolism of its main constituent, the phospholipid phosphatidyl-choline (6).

Glaucomatous visual impairment can be assessed through various computerized perimetry techniques such as standard achromatic perimetry and Fundus Automated Perimetry (7).

The morphological abnormalities of the retinal ganglion cells (RGCs) that give rise to the optic nerve and the optic nerve fibers (RNFL) can be detected through the use of Optical Coherence Tomography (OCT) (8).

Current functional evaluation techniques allow to quantify in a specific and differentiated way the dysfunctions of the various elements that form the optical pathway. In particular, through the Pattern electroretinogram (PERG) or the PhNR it is possible to quantify the functionality of the RGCs, while the nerve conduction along the optical pathways is objectivable through the recording of the Visual Evoked Potentials (VEP). Through the simultaneous recording of PERG and PEV it is possible to derive an electrophysiological index of post-retinal nerve conduction dysfunction: Retino-Cortical Time (RCT) (9).

By evaluating the RCT, it was hypothesized that in glaucoma the perimetric deficit is the result of two types of dysfunction: one at the level of the RGCs and the other at the level of the post-retinal optic pathway (10). The second dysfunction would be due to a reduction in nerve input from the RGCs on the cells of the Lateral Geniculate Nucleus (NGL) with a consequent reduction in bioelectric activity at the level of the occipital cerebral cortex (10).

Therefore mentioned post-retinal dysfunctions were supported by scientific evidence obtained thanks to the use of modern neuro-imaging techniques.

In fact, in recent years, neuro-imaging studies have shown in glaucoma patients a neuronal loss in the various structures that form the optical pathways and in particular at the level of the NGL (11-14), of the optic tract (12) and of the visual cortex. (13-16). Not only the structure, but also the functional connectivity of cortical neurocognitive networks is altered in glaucomatous patients, and

this aspect is not exclusive to visual networks, but also affects attentional and executive ones (17-18). This is to underline that a dysfunction of the visual system inevitably affects several other cognitive areas of the person.

In the current state of knowledge, it is not known whether in glaucomatous disease there is a relationship between electrophysiologically detected post-retinal nerve conduction dysfunction (10) and structural and functional changes in the NGL, optic tract or visual cortex (11- 16) and to what extent both the functional and structural changes of the post-retinal optical pathways are related to the morpho-functional modifications of the RGCs.

Since 1998, various studies have shown that in glaucoma patients treatment with Citicoline is able to induce a neuropotiation action with a consequent improvement in the functionality of RGCs (19-22) and a neuroprotection action with a consequent reduction in loss of RGCs and their nerve fibers (23, 24).

Furthermore, based on a neuromodulatory action, it was observed that treatment with citicoline administered intramuscularly or in oral suspension for a period of 2 months induced an improvement in nerve conduction along the post-retinal optic pathways indicated by a reduction of the RCT (19, 22).

Such multifactorial mechanisms of action may explain the reduction in the progression of perimetric glaucomatous deficit (24, 25).

In the current state of knowledge, it does not appear to have been studied whether the improvement in RCT detected after treatment with citicoline administered intramuscularly or in oral suspension (19, 22) can also be obtained with treatment with citicoline administered in oral solution.

Furthermore, it does not appear to have been evaluated whether there are structural and functional correlates [detectable with magnetic resonance methods in the various structures that form the optical pathways and in particular at the level of the NGL (11-14), of the optic tract (12) and of the cortex visual (13-16)] with the well-documented improvements in nerve conduction along the optical pathways obtained in glaucoma patients after treatment with Citicoline (19-22).

1.2 Citicoline mechanism of action

From the data available in the literature, it is known that the exogenous administration of citicoline causes an increase in endogenous phosphatidylcholine synthesis and thus accelerates the repair of the previously damaged cell membranes (26).

The cell membrane dysfunction or degeneration induces the release of cytotoxic substances (lyticenzymes, excitotoxic amino acids, etc.) which induce an extension of the area of damage or activate the mechanisms that lead to apoptosis (for example, an increase in the concentration of intracellular ceramide, a compound produced by catabolism of sphingolipids, is a potent proapoptotic agent).

In particular, in the etiology of vascular diseases (for example in stroke) a loss of phospholipid components is found resulting from an alteration in their metabolism, which leads to irreversible damage to the cell membranes of neurons. Biochemically a loss of phosphatidylcholine is observed, which is degraded during the ischemic processes into fatty acids with the production of reactive oxygen species (ROS).

Experimental studies suggest that the administration of citicoline induces a reactivation of the anabolism of the phospholipids with reduced degradation of phosphatidylcholine and thus reduced

formation of ROS. In some animal models a reduction was also observed of the infarcted area volume after treatment with Citicoline.

Therefore the therapeutic approach with citicoline allows the maintaining and/or restoring of the integrity of the cell membranes of neurons subjected to ischemic insults, such as can occur in some of the many forms of glaucomatous syndrome.

1.3. Neuro-functional considerations on treatment with Citicoline systemically and safety and tolerability in humans

The fundamental element for cell function and survival is the ability to maintain an internal environment different to the external one. This function is ensured by the cell membrane, a discriminating barrier that selects and regulates the passage of the substances inside the cell and controls the difference in electrical potential.

Also, most of the biochemical reactions occur close to the cell membrane and in its context surface receptors are located allowing a dialogue of the cell with the surrounding cells and the rest of the organism.

In fact, the cell membrane:

- is the site of receptors and synapses that govern communications with neighbouring cells and the rest of the organism,
- maintains and controls the difference in electrical potential, which is necessary to allow propagation of the nerve impulse,
- handles most enzymatic reactions, at the mitochondrial level, the inner membrane is the site of the main energy production processes.

A lesion of the cell membrane leads to three important events:

1. some ions normally concentrated in the extracellular environment, in particular Ca^{++} , and other potentially harmful molecules, can enter uncontrollably into the cytoplasm, altering the vital processes of the cell
2. the ability to communicate through surface receptors is lost;
3. the intracytoplasmic content, rich in lytic enzymes and toxic mediators, can flow outside of the cell resulting in an extension of the damage to the contiguous cells. Therefore, an alteration of the phospholipids turnover compromises the validity of the membrane protection systems. Furthermore, as a result of activating the particular lytic enzymes, the phospholipases, the catabolism of the membrane phospholipids is accelerated and, if the resynthesis mechanism is insufficient, toxic molecules accumulate, such as ceramide, which can activate the metabolic pathways that lead to programmed cell death (apoptosis). To maintain the perfect functionality of the cells, therefore, the cell membrane needs to stay structurally intact. This is absolutely necessary in the case of cells without replicative capacity like the RGC, the loss of which results in irreversible functional impairment.

The cell membrane is composed of a double layer of phospholipids. Phospholipids are continuously exposed to chemical and physical insults which damage the molecular structure: to protect itself from this, the cell possesses an enzyme system that catabolises the damaged phospholipids and reuses the constituent elements (phosphocholine, glycerol and fatty acids), in order to synthesise them again.

An alteration of the phospholipids turnover compromises the validity of the membrane protection systems and puts the specific cell functionality at risk. In the case of peripheral neurons such as RGC, the peculiar length of their axonal endings makes these cells particularly sensitive to any alteration in the cell membrane protection systems. In fact, precisely by virtue of the enormous

development of the membrane surfaces, due to the length of their axons, these cells are more susceptible than others to the harmful effects caused by a phospholipid synthesis slowdown.

The clinical conditions where a slowdown of the phospholipid metabolism occurs are those that present when the neural tissue undergoes a type of traumatic, ischemic or degenerative process. In glaucoma and in NAION a pathological situation is configured in which one or more of these 3 elements can contribute to the development of damage to the optic nerve. Both glaucoma and NAION are neurotrophicopathies where alterations of the retinal structures are observed (22, 27) and retinal structures (28).

An improvement of the VA, the VEP and contrast sensitivity after treatment with Citicoline was also observed in partially sighted patients (29-31). These studies suggested that the effects observed were attributable to the activity of dopamine-like effect of Citicoline (32, 33).

This pharmacological property, together with three other fundamental properties of this molecule [Neuroenhancement, neuroprotection and neurorestoration (34)] could explain the improvement of the morpho-functional condition of RGCs (35, 36) and of nerve conduction along the optical pathways (VEP with reduction of latency times) observed in glaucoma patients (19-22, 37).

In addition to the evaluation of retinal function, post-retinal nerve conduction was examined in glaucoma patients by measuring the RCT (38). The reduction in RCT, observed after treatment with Citicoline (19), can be attributed to an improvement in retinal function with consequent improvement of nerve conduction along the optical pathways and relative increase in bioelectric activity in those cells in which the cortical potential has its origin.

In addition to inducing an improvement in retinal bioelectric activity, Citicoline also produces neuroprotective effects, understood as a reduction in the progression of nerve fiber loss. This emerges from studies carried out in patients with ischemic optic neuritis treated with citicoline in oral solution (23) or from the results of a randomized clinical trial in which glaucoma patients were treated for 3 years with eye drops containing citicoline (24).

Therefore, these effects of Citicoline on the morpho-functional condition of RGCs and on the improvement of post-retinal nerve conduction, may explain the improvement of the visual field observed both in the first pioneering studies (20, 24, 25, 39, 40) and in studies more recent where improvement in perimetric indices (Mean Deviation-MD of Humphrey perimetry) are significantly correlated with an increase in PERG and VEP parameters (20, 41), it is likely that the previously mentioned sources of cortical improvement may also be suggested to explain the improvement.

In conclusion, everything reported suggests that Citicoline has a significant action in improving retinal and cortical bioelectric responses and in reducing the loss of peripillary nerve fibers in patients suffering from glaucomatous or ischemic optic nerve pathologies with consequent decrease in progression of perimeter damage.

To further advantage of this therapy, it should be emphasized that in no clinical study carried out in humans (19, 23, 25, 30, 31, 37, 42) are reported significant adverse reactions both ocular and systemic.

1.4 Rationale of the study

Considering that:

- 1) the visual field loss in glaucoma patients is attributable to a dysfunction of the RGCs associated with post-retinal nerve conduction delay (10),
- 2) the neuroradiological evaluations have highlighted changes in the nervous structures (NGL, optic tract, visual cortex) that form the optical pathways (11-18),
- 3) Citicoline possesses neuroenhancement and neuroprotection properties (34-36), with consequent improvement of nerve conduction along the optic pathways, reduction of the rate of progression of glaucomatous damage and maintenance of peripapillary nerve fibers (36),

we think that these assumptions constitute the rationale for carrying out a randomized clinical study that evaluates the effects of citicoline oral solution on the nerve conduction along the post-retinal optic pathways in glaucoma patients (information obtained through the registration of PERGs and VEPs and the calculation of the RCT) and if these effects have a morphological and functional correlation on the nervous structures that form the optical pathways (NGL, optic tract, visual cortex) (information obtained through the acquisition of structural and functional magnetic resonance).

These acquisitions will allow us to assess how much post-retinal nerve conduction and the structural integrity of the optical pathways are influenced by changes in the morpho-functional state of the RGCs.

2. OBJECTIVES AND AIMS OF THE STUDY

- 1) Primary Objective: to evaluate whether treatment with **Citicoline in oral solution** can produce an improvement of the post-retinal nerve conduction, altered base in patients with OAG.
- 2) Secondary objective: to evaluate in patients with OAG whether the possible changes in post-retinal nerve conduction induced by treatment with Citicoline in oral solution (information obtained through electrophysiological recordings) are associated or not with **morphological and functional variations of the nervous structures that form the optical pathways** (NGL, optic tract, visual cortex, information obtained through the acquisition of structural and functional magnetic resonance imaging) and whether both conditions can be related to the morpho-functional variations of the RGCs and of the visual field (CV).

4. STUDY POPULATION

Sixty patients affected by bilateral OAG, between the ages of 20 and 70, will be enrolled in the study within a maximum time frame of 12 months (see point 9.1 "sample size").

4.1 Inclusion criteria:

- Age between 20 and 70 years old
- Diagnosis of glaucoma. Glaucoma is defined as: glaucomatous damage of the CV (Humphrey 24-2 standard SITA with mean deviation between -6 and -25 dB) and glaucomatous appearance of the optic nerve
- Visual acuity not less than 5/10

- Eye pressure below 21 mmHg with the use of ocular hypotonizing drugs including sympathomimetics, beta-blockers, prostaglandins, beta-adrenergics, carbonic anhydrase inhibitors. Such drugs can be used both alone and in combination with each other.
- Documented post-retinal nerve conduction delay through simultaneous recording of VEP and PERG showing an increase in RCT

4.2 Exclusion criteria:

- Ocular surgery in the 3 months preceding the study, including surgery for cataracts in the previous three months.
- Cataract or maculopathy
- Argon laser trabeculoplasty (ALT) within the previous 6 months
- Known hypersensitivity to the study product
- Secondary causes of ocular hypertension, including systemic or topical use of steroids
- Positive history of ocular or systemic diseases that could preclude enrollment in the study in the opinion of the investigators
- Changes in systemic therapies that could compromise intraocular pressure values (beta-blockers, alpha and beta adrenergics, calcium inhibitors, ACE inhibitors) in the 30 days prior to enrollment
- Ongoing therapy with vasoactive cerebral drugs, neurotrophic, lutein, zeaxanthin, retinal, acid, docosahexaenoic, Ubiquinone and / or its derivatives, Citicoline and / or its derivatives (possible previous treatment with Ubiquinone, L-Carnitine, Citicoline and / or its derivatives must have been suspended at least 6 months prior to inclusion in the study)
- Pregnancy, breastfeeding
- Diabetes
- Systemic lupus erythematosus, rheumatoid arthritis, connectivitis
- Concomitant use of anticoagulants and lithium

5. EXPERIMENTAL DESIGN

5.1 Experimental plan

A prospective, multicentre, randomized, blinded, masked study that involves the enrollment of a minimum of 60 (see sample size in paragraph 9 "Statistical Analysis") affected by OAG.

Patients selected according to the inclusion / exclusion criteria, after signing the informed consent, will be randomized into two groups:

a) In a group of patients with OAG, **Citicoline in oral solution (10 ml / day, Neurotidine®)** will be administered for 12 months (Citicoline Treated Group, TC Group)

b) in another group of patients with OAG will be **administered Placebo** (Containing all excipients of Neurotidine ®) (10 ml / day) for 12 months (Placebo Treated Group, TP Group)

Randomization will be done by dividing the selected patients into two groups based on similar characteristics of: age, perimetric defect and, mainly, RCT values.

Patients will be assigned to each group by an investigator not involved in functional and structural

testing.

The key will be opened only at the end of the treatment in order to evaluate the first effects.

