5.4 Planned visits

The visits will be performed at T0 (screening), at T1 (baseline, 7-15 days after T0), after 6 months (T2) and after 12 months (T3) of follow-up not knowing which group the subject belongs to.

After screening (T0), enrolled patients will perform a baseline visit (T1) during which they will be randomized to one of the two groups. The visits will take place 6 and 12 months after the baseline visit.

A complete eye examination will be performed at T0, T1, T2 and T3 including the following assessments: corrected visual acuity, biomicroscopy, indirect ophthalmoscopy, intraocular pressure measurement with Goldmann applanation tonometer, CV test, recording of PERGs and VEPs, imaging of the optic nerve and retinal nerve fiber layer by OCT. Neuroradiological evaluation will also be performed at T1 and T3.

At the end of the T1 visit, the patient will be given 4 bottles containing 500 ml Neurotidine® or Placebo and will be given the relative instructions for administration. The regimen will be 1 administration of 10 ml once a day for 6 months. Each bottle can be used for 50 days. At the end of the 6 month period the patient will be asked to hand over the used bottles.

After 6 months \pm 10 days (T2), patients will be given an additional 4 bottles containing Neurotidine® or Placebo and will be given instructions for their administration. The regimen will be 1 administration of 10 ml once a day for 6 months. Each bottle can be used for 50 days. Again at the end of this 6 month period the patient will be asked to hand over the used bottles.

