6. ASSIGNMENT AND MASKING

Patients with OAG will be selected from a large cohort of already known diseases and followed at our facility for at least 12 months.

Only patients who meet the inclusion criteria will be selected. Patients will undergo a baseline screening visit during which conditions corresponding to the inclusion criteria will be assessed and the study will be proposed.

Only after the signing of the informed consent, a single investigator ("enrolling physician"), not involved in the clinical and instrumental evaluations, will decide whether to assign the selected patient to one of two groups: treated-Citicoline or treated-Placebo.

The assignment to one or the other group will take place in sequential order of presentation of the patient (with a 1: 1 probability of joining one or the other group) in order to constitute two homogeneous groups in number.

The aforementioned assignment will not be known to the patient and will not be known to the "enrolling physician".

Consequently, during the entire duration of the study (both at the baseline visit and at the 6 and 12 month visit), all evaluations foreseen by the study will be carried out by investigators who will not know whether the patient being examined belongs to the Citicoline-treated group or treated-Placebo.

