7.10 Compliance with treatment

The importance of regularly assuming what is assigned by the "recruiting physician" (Neurotidine® or Placebo) must be emphasized by the Investigator to the patient, who, based on the signature of the informed consent, must also be instructed to return, during the follow-up visits following the delivery date, according to the timing of the study, the unused and / or surplus samples (bottles).

In this way, the Investigator will be able to fill in, both during the control visits and at the end of the trial, the section of the CRF in which compliance with the prescription is recorded, calculate the compliance with the treatment and provide for the conservation of the material returned in a place accessible only to authorized persons.

At T2 and T3 compliance will be assessed by counting the quantity of product returned by the patient because it is not used and calculating the ratio between the number of quantities taken and the quantity that should have been taken according to the dosage schedule provided by the protocol.

Based on compliance, all patients who have taken at least 80% of the prescribed dosage regimen will be considered compliant with the treatment.

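### The allocation text contradicts itself: the enrolling physician both decides the arm and does not know it, and section 5.1 describes randomization without a chance mechanism, so random, concealed allocation is not assured as written

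*Protocol*

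**What the plan says.** Four sections of the protocol describe allocation.

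- **Section 5.1** calls the study randomized and then gives the method: "Randomization will be done by dividing the selected patients into two groups based on similar characteristics of: age, perimetric defect and, mainly, RCT values". It adds that the person assigning patients takes no part in the functional and structural tests, and that a key is opened only when treatment ends.
- **Section 5.4** (with the schedule in 5.2) places the step at each patient's own visit: "enrolled patients will perform a baseline visit (T1) during which they will be randomized to one of the two groups".
- **Section 6** says that a single enrolling physician, not involved in the evaluations, "will decide whether to assign the selected patient to one of two groups: treated-Citicoline or treated-Placebo". Next comes "The assignment to one or the other group will take place in sequential order of presentation of the patient", with 1:1 probability, "in order to constitute two homogeneous groups in number". It then says that the assignment "will not be known to the patient and will not be known to the" enrolling physician. The patients are "selected from a large cohort of already known diseases and followed at our facility for at least 12 months".
- **Section 7.10**, on compliance, refers to "what is assigned by the 'recruiting physician' (Neurotidine® or Placebo".

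Three further details bear on the reading. The placebo cannot be told from the active product by look or taste (7.2). The case report form carries a randomization number (12.1). Enrolment runs over up to 12 months (4 and 5.3).

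**The concern.** The primary comparison is the change in RCT between the two arms (section 5.5). Its validity rests on the arm being set by chance and on nobody being able to foresee or influence it before the patient is committed. Followed literally, two sentences allow a person to choose: the one that gives the decision to the enrolling physician, and the one that divides patients by their characteristics.

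The patients come from a cohort that the facility has followed for at least 12 months, so whoever assigns may know more about prognosis than the recorded covariates show. An imbalance in measured baseline RCT can be adjusted for in the analysis. Steering on an unmeasured feature cannot, and masking after assignment does not undo it.

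**Working it through.** **The passages side by side**

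1. *Who chooses.* Section 6 gives the choice between two named treatments to the enrolling physician and, a few lines later, says that this physician does not know the assignment. A person cannot choose between named arms and be unaware of the choice. One of the two statements must be wrong. Section 7.10 again attributes assignment to a physician, apparently in the same role. That sentence is about adherence and is weak evidence alone.
2. *How.* Section 5.1 sorts patients on age, field defect and mainly RCT, and its sentence states no chance element, order or probability. Section 6 gives an order and a 1:1 probability, but no balancing on RCT. Section 5.4 allocates each patient at T1, and enrolment takes up to 12 months, so there is no complete consented group to divide at one time.
3. *Can they be reconciled?* Yes, by randomization stratified or minimised on the named factors, issued as coded bottles at T1. The key, the matching placebo and the randomization number fit this. But no available part of the protocol mentions a pre-generated sequence, stratification, minimisation or a holder of the code.

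**Illustration of what is at stake (assumed inputs, not an estimate)**

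From section 9.1: 27 evaluable per arm, 30 after 10% drop-out (27 / 0.9 = 30); RCT 70.21 ± 9.12 ms at baseline and 63.3 ± 8.15 ms at the end, a difference of 6.91 ms. The stated 27 is consistent with these inputs. At two-sided 5% and 80% power, the pooled SD of 8.65 gives 25–26 per arm and an SD of 9.12 gives 28–29. The allocation point does not depend on this.

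Assumed: half the patients share an unmeasured feature worth D = 4 ms of 12-month RCT. They receive citicoline with probability p = 0.75, and the others with probability 0.25. The drug has no effect. The analysis adjusts for baseline RCT, with a baseline-to-12-month correlation r of 0.5 to 0.7.

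- False difference = (2p − 1) × D = 0.5 × 4 = 2 ms, which is 2 / 6.91 = 29% of the planning difference.
- Standard error = 8.15 × √(1 − r²) × √(2/27) = 1.92, 1.77 and 1.58 ms for r = 0.5, 0.6 and 0.7.
- Noncentrality = 2 / SE = 1.04, 1.13 and 1.26.
- Two-sided 5% test on 54 − 3 = 51 degrees of freedom (noncentral t): rejection probability 17.5%, 19.8% and 23.6%, against 5% with no steering.

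**Consequence of stratifying on RCT for the analysis**

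Stratification removes most of the chance difference in baseline RCT between arms, but an unadjusted t-test on change still counts that variation in its standard error. The slope of change on baseline is r × 8.15 / 9.12 − 1, which is −0.55 at r = 0.5 and −0.37 at r = 0.7. I simulated 20,000 null trials of 60 patients, in blocks of 4 within thirds of RCT. The unadjusted test's false-positive rate was about 2.5–3% (2.3% at r = 0.5 to 3.1% at r = 0.7). With baseline RCT in the model it was 4.9–5.3%.

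**The case against.** The best defence is that this is loosely translated text around a sound intention. In section 5.1 the selected patients are simply those who meet the criteria, not a pool assembled for one division. The subject of the sentence is randomization, and section 6 gives a 1:1 probability. Stratified or minimised allocation at T1 would satisfy sections 5.1, 5.4 and 6 together. The assigning person does no testing, the placebo is indistinguishable and the key stays closed, so steering at the assumed strength needs an assigner who knows the arm.

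Much of this stands. The mismatch between sections 5.1 and 6 can be reconciled and is a failure of alignment more than a flat contradiction. Balancing on RCT is legitimate. Masking after assignment is stated consistently. The steering figure applies only if the unfavourable half of section 6 is the half that operates.

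It does not remove the clash inside section 6. Nor does an indistinguishable placebo show that the arm was set by chance.

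Two stronger readings are tempting. A reader might infer that allocation was in fact non-random. The documents do not support that, since they call the study randomized, state a probability and mention a key. A reader might also take section 6 as an unrestricted coin toss and calculate the expected imbalance in numbers or in RCT. The protocol never says unrestricted. It states an aim of equal numbers and names balancing factors, both of which point to restriction, so such figures would test a scheme that the protocol does not describe.

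**Conclusion.** Wrong as written, and to be corrected. Section 6 cannot be followed as it stands, and section 5.1 is not aligned with it. Random, concealed allocation is therefore not assured by the text. This is a conflict between sentences that the protocol contains, not detail that could be left to an analysis plan. The front pages and the text between sections 2 and 4 were not available. They might add a method, but they would not remove the conflicting sentences.

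The size is conditional. If someone did steer, with the assumed 2 ms effect, the false-positive rate would be about 18–24% instead of 5%. The figure rests on assumed values of p, D and r, and the conclusion does not depend on it.

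**What to change.** Remove from section 6 the wording that gives the physician the decision, remove from 5.1 the wording about dividing selected patients, and reword 7.10 so that no physician is said to assign the product. State one rule in all three places, consistent with 5.4:

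- a computer-generated random sequence prepared in advance, in permuted blocks, stratified by baseline RCT at cut-points fixed beforehand, with one sequence per stratum;
- centre handled explicitly, because section 5.1 calls the study multicentre, for example as a stratum or by central allocation across centres;
- the sequence held by someone outside enrolment and assessment;
- identical pre-numbered bottles, with the enrolling physician only registering the patient at T1 and receiving a kit number, linked to the randomization number already foreseen in 12.1.

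If age and field defect must also be balanced at allocation, use centrally run minimisation with a random element. That needs a live allocation service and costs more.

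Include baseline RCT in the between-arm primary analysis. Otherwise an unadjusted comparison of change would be conservative after stratification, as the simulation shows.

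Cost: rewording three sections, preparing the sequences, labelling kits and a little staff time to hold the code. No patients or visits are added.
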